# 5.2 ASSESSMENT OF SAFETY

Safety will be assessed descriptively based on the following observations and examinations:

- Physical examination
- Vital signs
- Clinical laboratory values (haematology, clinical chemistry, coagulation, infection testing and urinalysis)
- 12-lead ECG
- AEs
- Serious AEs (SAEs)
- Intensity of AEs assessed by CTCAE grading version 5.0 (refer to ISF for details)
- Suicidality

The detailed corresponding observations and examinations are described in the following respective subsection.

# 5.2.1 Physical examination

Physical examinations will be performed at the time points specified in the Flowchart.

A complete physical examination will be performed at screening. It includes at a minimum general appearance, neck, lungs, cardiovascular system, abdomen, extremities, and skin.

For subsequent visits, targeted physical examinations will be done. Targeted physical examination should include examination of the skin (involved areas) and examination pertinent to adverse events or abnormal results from lab test, ECG and/or vital signs.

Measurement of height and body weight will be performed at the time-points specified in the Flowchart. BMI will be automatically calculated.

The results must be included in the source documents available at the site.

# 5.2.2 Vital signs

Vital signs will be evaluated at the time-points specified in the Flowchart. This includes temperature, respiratory rate, systolic and diastolic blood pressure, and pulse rate (electronically or by palpation count for 1 minute). The results must be included in the trial participant's source documents. Measurement of vital signs should precede blood sampling at all visits.

At dosing visits, vital sign evaluations will be performed pre-dose and additional evaluations will be taken post-dose, approximately 5 and 60 minutes after The investigator should evaluate the clinical significance of the results. Clinically abnormal findings will be reported as baseline condition or AEs.

Page 79 of 177

Proprietary confidential information © 2023 Boehringer Ingelheim International GmbH or one or more of its affiliated companies

At dosing visits for	administrat	ion, vital signs e	valuations will be
performed pre-dose an	d, again, approximately 10 r	ninutes after the	end of drug
administration. At Visi	t 6 and	Visit 7	additional
measurements will be	performed approximately 60	) minutes post-de	ose
	•	-	

# **5.2.3** Safety laboratory parameters

Safety laboratory parameters to be assessed are listed in Table 5.2.3: 1. For the sampling time-points, please see the Flowchart. More frequent blood sampling than the defined in the Flowchart may be done whenever the investigator deems necessary. Unscheduled safety laboratory examinations will be reported in the CRF along with the results.

It is preferred, but trial participants do not have to be fasted for the blood sampling for the safety laboratory. Instructions regarding sample collection, sample handling/processing, and sample shipping are provided in the Laboratory Manual in the ISF.

All analyses will be performed by a central laboratory, and the respective reference ranges will be provided in the ISF.

The central laboratory will send reports to the investigator. It is the responsibility of the investigator to evaluate the laboratory reports. Clinically relevant abnormal findings as judged by the investigator will be reported as baseline conditions or AEs (please refer to Section 5.2.6). A clinically relevant value may be either in- or outside the reference range. Clinically relevant abnormal laboratory test results must be confirmed and should be repeated until normalisation or stabilisation or until an alternative explanation has been found. Abnormal laboratory values will be graded for intensity by using CTCAE Version 5.0 criteria.

In case the criteria for hepatic injury are fulfilled, a number of additional measures will be performed (please see Section 5.2.6.1 and the DILI Checklist provided in the ISF. The amount of blood taken from the trial participant concerned will be increased due to this additional sampling.

40061625-02 Clinical Trial Protocol Page 80 of 177

Proprietary confidential information © 2023 Boehringer Ingelheim International GmbH or one or more of its affiliated companies

Safety laboratory tests Table 5.2.3: 1

Functional lab group	Test name	
Haematology	Hematocrit (Hct)	
	Hemoglobin (Hb)	
	Glycosylated Hbc (HbA1c) (Only at baseline)	
	Red Blood Cell Count/Erythrocytes	
	Reticulocyte Count	
	White Blood Cells/Leukocytes	
	Platelet Count/Thrombocytes	
Diff. Automatic	Neutrophils (relative and absolute count)	
	Eosinophils (relative and absolute count)	
	Basophils (relative and absolute count)	
	Monocytes (relative and absolute count)	
	Lymphocytes (relative and absolute count)	
Diff. Manual (if Diff Automatic is	Neutrophils, bands (Stabs)	
abnormal)	Neutrophils, polymorphonuclear (PMN)	
	Eosinophils	
	Basophils	
	Monocytes	
	Lymphocytes	
Coagulation	Activated Partial Thromboplastin Time (aPTT)	
	Prothrombin time (INR)	
	Fibrinogen	
Enzymes	AST (GOT)	
	ALT (GPT)	
	Alkaline Phosphatase (AP)	
	Creatine Kinase (CK)	
	CK-MB, only if CK is elevated	
	Gamma-Glutamyl Transferase (GGT/γ-GT)	
	Lactic Dehydrogenase (LDH)	
	Amylase	
	Lipase	
Electrolytes	Calcium	
	Sodium	
	Potassium	
	Chloride	

40061625-02 Clinical Trial Protocol Page 81 of 177

Proprietary confidential information © 2023 Boehringer Ingelheim International GmbH or one or more of its affiliated companies

Safety laboratory tests (cont.) Table 5.2.3:1

Functional lab group	Test name
Substrates	Glucose
	BUN (blood urea nitrogen)
	Uric acid
	Creatinine 
	eGFR (estimated by CKD-EPI formula) (only at screening)
	Bilirubin Total
	Bilirubin Direct (if total is elevated)
	Bilirubin Indirect (if total is elevated)
	Troponin (Reflex, in case of elevated CK)
	Protein, Total
	Albumin
	C-Reactive Protein (CRP and hs-CRP [high sensitivity – CRP])
	Cholesterol, total
	Triglycerides
	LDL-Cholesterol
	HDL-Cholesterol
Specific gamma-globulin quantification	$IgE^1$
Hypersensitivity	Complement C3
	Complement C4
	Complement total
	Histamine
	Tryptase
Urine Pregnancy test (only for female patients of childbearing potential)	Human Chorionic Gonadotropin in urine
Serum Pregnancy test (only for female patients of childbearing potential at screening. At later visits only if urine pregnancy test is positive)	Human Serum Chorionic Gonadotropin
Hormones (only at screening)	TSH (free T3 and free T4 in case of abnormal TSH result)
Urinalysis (dipstick)	Urine Nitrite
· · · · · · · · · · · · · · · · · · ·	Urine Protein
	Urine Glucose
	Urine Ketone
	Urobilinogen
	Urine Bilirubin
	Urine RBC/Erythrocytes
	Urine WBC/Leukocytes
	Urine pH

Page 82 of 177

Proprietary confidential information © 2023 Boehringer Ingelheim International GmbH or one or more of its affiliated companies

Table 5.2.3:1 Safety laboratory tests (cont.)

Functional la	ab group	Test name		
Urine-Sediment (microscopic examination,		Urine Sediment Bacteria		
only if urine a	analysis abnormal)	Urine Cast in Sediment		
		Urine Squamous E	pithelial Cells	
		Urine Sed. Crys., U	Inspecified	
		Urine Sediment RBC/Erythrocytes		
	Urine Sediment WBC/Leucocytes			
Urine (only a	Urine (only at screening)  Albumin (quantitative)		ive)	
Infection Tes	ting	See Table 5.2.3: 2		
1 Only in case	1 Only in case of allergic reaction			
2 Creatinine ca	an be measured by any of the three	serum creatinine assays	s listed in the table below:	
Short name	Name of serum creatinine assay	Substrate	Other information	
CREE	Creatinine, enzymatic	creatinine	Enzymatic	
CREJIDMS	Creatinine, Jaffe, IDMS	creatinine	Jaffe reaction, IDMS standardised	
CREJ	Creatinine, Jaffe, Not IDMS	creatinine	Jaffe reaction, Not IDMS standardised	

Table 5.2.3: 2 Exclusionary laboratory tests (including infection and pregnancy testing)

Functional lab group	Test name
Infection Testing	Hepatitis B Surface Antigen (qualitative)
	Hepatitis B Surface Antibody (qualitative) (Only for Japan)
	Hepatitis B core Antibody (qualitative)
	HBV-DNA PCR (quantitative) at screening (Visit 1) and EOT Visit 
	Hepatitis C Antibody (qualitative) 
	HIV-1, and HIV-2 Antibody (qualitative)
	QuantiFERON®-TB-Gold Plus, 2,3,4,5
	T-spot TB test
Serum pregnancy test (only for female trial participants of childbearing potential)	Human Serum Chorionic Gonadotropin

 A HBV-DNA PCR should be done if Hepatitis B core Antibody is positive and Hepatitis B Surface Antigen is negative. These evaluations should be conducted at screening and at the EOT visit. (Only for Japan: a HBV-DNA PCR should be done if Hepatitis B core Antibody and/or Hepatitis B Surface Antibody is positive and Hepatitis B Surface Antigen is

# Boehringer Ingelheim BI Trial No.: 1368-0098

c40061625-02 Clinical Trial Protocol

Page 83 of 177

Proprietary confidential information © 2023 Boehringer Ingelheim International GmbH or one or more of its affiliated companies

negative. These evaluations should be conducted at screening and at the EOT visit. If HBV DNA level is undetectable at screening, the patient can participate in this trial. But HBV DNA level will be monitored at least every 6 months.)

- 2 There is the trial site option to perform a PPD skin test. (Only for Japan: Chest X-ray test or CT chest should be done if not done within 3 months prior to Visit 1.)
- 3 Trial participants with indeterminate QuantiFERON or invalid/borderline T-spot may be retested with IGRA (once) and if inconclusive should have a PPD skin test.
- 4 In trial participants with a negative IGRA or PPD skin test, the test should be repeated at the EoT visit. Results of the PPD test should be collected in the CRF.
- 5 Only for South Africa: Additionally, the tuberculosis infection testing will be repeated approximately 6 months from baseline On clinical suspicion of Tuberculosis, infection testing can be performed as per the investigator's discretion at any time during the study.
- 6 Positive Hepatitis C antibody should be confirmed with Hepatitis C RNA PCR.

The investigator will use the exclusionary lab test results for the assessment of the participants' eligibility for the trial. The infection testing will be repeated at EoT visit as per defined criteria.

# 5.2.4 Electrocardiogram

The 12-lead ECGs must be administered by a qualified technologist and results will be recorded as scheduled in the Flowchart. The investigator or a designee will evaluate whether the ECG is normal or abnormal and assess clinical relevance. ECGs may be repeated for quality reasons. Additional ECGs may be recorded for safety reasons. Dated and signed printouts of ECG with findings should be documented in participant's medical record.

Clinically relevant abnormal findings will be reported either as baseline condition (if identified at the screening visit) or otherwise as AEs and will be followed up and/or treated as medically appropriate.

# 5.2.5 Other safety parameters

Trial participants with a history of malignancy (except for specific cancers) will be excluded from this trial per the exclusion criteria (Section 3.3.3). All cases of malignancies that are detected during the trial will be reported as SAEs, see Section 5.2.6.

# 5.2.5.1 Local tolerability

Local tolerability at the administration site of trial medication will be assessed by the investigator during the study drug administration visit and at the time of AE assessment by questioning retrospectively since the last visit. Any observed local tolerability reaction, e.g. "swelling", "induration", "heat", "redness", "pain", and other findings should be reported as an adverse event, see Section 5.2.6.

Suicidal thoughts and behaviour will be assessed by the Columbia-Suicide Severity Rating Scale (C-SSRS) [R08-1147]. The C-SSRS is a semi-structured, investigator-rated interview, developed by clinical experts in cooperation with the FDA, assessing both suicidal behaviour and suicidal ideation. It does not give a global score but provides some categorical and some severity information specifically for behaviour and ideation.

# **Clinical Trial Protocol**

Page 84 of 177 Proprietary confidential information © 2023 Boehringer Ingelheim International GmbH or one or more of its affiliated companies

The baseline/screening scale of the C-SSRS will be administered for eligibility confirmation and the follow-up scale at all visits for assessment of suicidality.

The C-SSRS interview may be administered by any type of physician, psychologist, clinical social worker, mental health counsellor, nurse, or coordinator with C-SSRS training. It has a typical duration of five minutes and causes only a low burden on trial participants. At a minimum, the interview consists of 2 screening questions related to suicidal ideation and 4 related to suicidal behaviour and may be expanded to up to 17 items in case of positive responses. Free text entries are allowed for; the investigator has to directly evaluate the scale and write a report. In this trial, paper forms will be used for the assessment of the C-SSRS, and results will be transcribed into the e-CRF.

The C-SSRS has been widely used in large multinational clinical trials. The C-SSRS will be administered at the Screening Visit/Visit 1 (using the 'baseline/screening' version) with the aim to exclude patients with active moderate to severe symptomatology within a specified time prior to the screening or screening visit. The lifetime and the past year history of suicidal ideation and behaviour will also be recorded. After the screening visit, the assessment 'since last visit' version will be performed at each visit. The investigator is to review positive and negative reports for plausibility and clinical relevance. Doubtful reports may be repeated, or reports may be validated by a consulting psychiatrist or other mental health professional expert. If there is a confirmed positive report of suicidal behaviour or suicidal ideation type 4 or 5 after start of trial (see Section 3.3.4.1 for reference about discontinuation), the investigator is to immediately interview the trial participant and/or is to consult a mental health professional. If the positive report is confirmed, appropriate actions for the trial participant's safety have to be initiated.

All C-SSRS reports of suicidal ideation type 4 or 5 and all reports of suicidal behaviour must be reported as separate SAEs by the investigator. For 'Self-injurious behaviour, without suicidal intent', standard AE/SAE reporting rules are to be applied. For each negative report (suicidal ideation type 1, 2, or 3) after the start of the trial, the investigator is to decide on the basis of clinical judgment whether it represents an AE as defined in the protocol, and if it is considered an AE, then it must be reported accordingly.

#### 5.2.6 Assessment of adverse events

Data and information necessary for the thorough assessment of AEs, SAEs, and AESIs will be reported to the sponsor via eCRF. This may include specific data and information not prospectively specified in this protocol.

#### 5.2.6.1 Definitions of AEs

#### 5.2.6.1.1 Adverse event

An AE is defined as any untoward medical occurrence in a trial participant or clinical investigation subject administered a medicinal product and which does not necessarily have to have a causal relationship with this treatment.

# Clinical Trial Protocol

Page 85 of 177

Proprietary confidential information © 2023 Boehringer Ingelheim International GmbH or one or more of its affiliated companies

An AE can therefore be any unfavourable and unintended sign (including an abnormal laboratory finding), symptom, or disease temporally associated with the use of a medicinal product, whether considered drug-related or not.

The following should also be recorded on the appropriate eCRFs, BI SAE form (if applicable):

- Worsening of the underlying disease (for definition, see Section 4.2.3) or of other pre-existing conditions.
- Changes in vital signs, ECG, physical examination, and laboratory test results, if they are judged clinically relevant by the investigator.

If such abnormalities already exist prior to trial inclusion, they will be considered as baseline conditions and should be collected in the eCRF only.

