#### Safety

Occurrence of treatment emergent adverse events (TEAEs)

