#### 4.2.3 Concomitant medications/interventions

The following sections provide definition of certain terms used in this trial and additional information on certain concomitant medications and lesion interventions. The sponsor will not provide/supply these treatments to the sites.

Any medication received by trial participant from Visit 1 should be recorded in the appropriate concomitant medications page in the eCRF.

**Rescue medication** is defined as the treatment for HS disease worsening and includes systemic antibiotics and/or immunosuppressive biologics such as TNF-inhibitors.

**HS Disease worsening** is defined as total AN count is 150% of baseline AN count. For example, for a baseline AN count of 10, disease worsening should be interpreted as an AN count of 15 and above.

Page 72 of 177

Proprietary confidential information © 2023 Boehringer Ingelheim International GmbH or one or more of its affiliated companies

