#### 7.2.6 Safety analyses

Adverse events will be coded using the Medical Dictionary for Drug Regulatory Activities (MedDRA). Standard BI summary tables and listings will be produced. All adverse events with an onset between start of treatment and end of the REP, a period of 16 weeks after the last dose of trial medication, will be assigned to the on-treatment period for evaluation.

The safety analysis will be performed by treatment at onset.

Safety analyses will be based on the TS. In general, safety analyses will be descriptive in nature and will be based on BI standards. No hypothesis testing is planned.

Statistical analysis and reporting of adverse events will concentrate on treatment-emergent adverse events, i.e. all adverse events occurring between start of treatment and end of the REP. Adverse events that start before first drug intake and deteriorate under treatment will also be considered as 'treatment-emergent'. Adverse events will be summarized by treatment at onset, and the treatment at onset of AE for the drug-related AE.

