7.8.1 Adverse Events

Date: 07-08-2024, Version 1.0

Unless otherwise specified, the analyses of AEs will be descriptive in nature, which will include all on-treatment events up to week 8, week 16 treatment, as well as all events during the whole on-treatment period respectively. All analyses of AEs will be based on the number of subjects with AEs and NOT on the number of AEs.

AEs will be coded with the most recent version of MedDRA®. Patients will be analyzed according to the actual treatment received.

The analysis of AEs will be based on the concept of treatment emergent adverse events (TEAE). That means that all AEs occurring between first drug intake till 112 days after last drug intake will be assigned to the on-treatment period. All AEs occurring before first drug intake will be assigned to 'screening' and all AEs occurring after last drug intake + 112 days will be assigned to 'follow-up' (for listings only). For details on the treatment definition, see Table 6.1:1.

The exposure adjusted incidence rate (per 100 patient years) of a selected treatment emergent adverse event is defined as the number of patients experiencing the adverse event per

Proprietary confidential information © 2024 Boehringer Ingelheim International GmbH or one or more of its affiliated companies.

treatment group during time at risk divided by the total time of patients at risk in that treatment group to contribute the event to the analysis multiplied by 100 (per 100 patient years).

Time at risk [patient years] = (date of onset of AE– first treatment start date within that treatment period + 1) / 365.25

If, for a patient, the selected treatment emergent adverse event didn't occur during the above defined treatment period (per Table 6.1:1) then the time at risk will be censored at the earliest of date of death, last contact date per EoS page, or the end of the above defined treatment period.

For each selected treatment emergent AE, the exposure adjusted incidence rate will be calculated as:

Incidence rate [1/100 Patient years (pt-yrs)] = 100 * number of patients with TEAE / Total TEAE-specific time at risk [patient years].

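### HS worsening, defined by lesion count alone, is recorded under the AE definition and not removed from TEAEs, so the any-TEAE comparison can flatter spesolimab if it reduces AN worsening

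*Protocol*

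**What the plan says.** Protocol Section 5.2.6.1.1 (Adverse event) follows its AE definition with a list introduced by "The following should also be recorded on the appropriate eCRFs, BI SAE form (if applicable"). The first item is "Worsening of the underlying disease (for definition, see" Section 4.2.3). In Section 4.2.3, HS disease worsening "is defined as total AN count is 150% of baseline AN count"; the example given there (baseline 10, worsening at 15 and above) shows that this means 150% or more. No symptom, treatment need or draining tunnel (dT) count enters the definition.

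Protocol Section 2.1.3 gives one Part 1 secondary safety endpoint: "Occurrence of treatment emergent adverse events (TEAEs"). SAP 5.2.2 repeats it. Protocol 7.2.6 defines TEAEs as "i.e. all adverse events occurring between start of treatment and end of the REP". SAP 7.8.1 states that "all AEs occurring between first drug intake till 112 days after last drug intake will be assigned to the on-treatment period" and that "All analyses of AEs will be based on the number of subjects with AEs and NOT on the number of AEs". Neither text sets the study disease apart.

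SAP 7.8.1 plans an overall AE summary, a summary by maximum CTCAE intensity, and tables by system organ class and preferred term. Drug-related AEs, SAEs, AEs leading to discontinuation, AESIs, other significant AEs and user-defined concepts also get separate tables. None of the listed user-defined concepts covers HS worsening.

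**The concern.** The event recorded under the AE definition is already used on the efficacy side. It is the protocol's condition for rescue medication (Section 4.2.3), and it overlaps with the HS flare endpoint, which is built on the same AN count. One component of the safety endpoint therefore falls when efficacy on AN improves.

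If spesolimab lowers AN worsening, placebo participants enter the any-TEAE count more often for lack of efficacy. A true excess of other adverse events on drug then looks smaller, disappears or changes sign. With three doses, the size of the shift can differ between arms. Primary objective 2 weighs safety and efficacy together in choosing the Part 2 dose, so readers of the safety summary need to know how much of any difference is disease worsening.

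**Working it through.** The documents state no TEAE rate and no worsening rate, so there is no plan figure to reproduce. The structure can be checked exactly; the size can only be illustrated.

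**Overlap with the flare endpoint.** Worsening needs AN of at least 1.5 × baseline. Flare (Protocol 2.2.2) needs a rise of at least 25% and at least 2 lesions. With whole-number counts:

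| Baseline AN | Worsening at | Flare at |
|---|---|---|
| 3 | 5 | 5 |
| 4 | 6 | 6 |
| 5 | 8 | 7 |
| 10 | 15 | 13 |
| 20 | 30 | 25 |

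From a baseline AN of 3 upward, every visit that meets the worsening definition also meets the flare definition.

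**Effect on any TEAE.** Let t be the risk of any other TEAE and w the risk of recorded HS worsening, assumed independent. Then P(any TEAE) = 1 − (1 − t)(1 − w). All rates below are assumptions; differences are drug minus placebo, in percentage points.

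| t placebo / drug | w placebo / drug | Any TEAE placebo / drug | Difference without worsening | Difference with worsening |
|---|---|---|---|---|
| 60 / 60 | 15 / 10 | 66 / 64 | 0 | −2 |
| 60 / 60 | 20 / 10 | 68 / 64 | 0 | −4 |
| 60 / 60 | 30 / 15 | 72 / 66 | 0 | −6 |
| 60 / 60 | 20 / 20 | 68 / 68 | 0 | 0 |
| 60 / 64 | 20 / 10 | 68 / 67.6 | +4 | −0.4 |
| 50 / 60 | 20 / 10 | 60 / 64 | +10 | +4 |
| 50 / 60 | 30 / 10 | 65 / 64 | +10 | −1 |
| 50 / 60 | 20 / 20 | 60 / 68 | +10 | +8 |

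Example, second row: 1 − 0.40 × 0.80 = 0.68 and 1 − 0.40 × 0.90 = 0.64. With t equal in both arms, the shift is (1 − t)(w drug − w placebo), which is zero when w is equal. With w equal, a true difference is multiplied by (1 − w): +10 becomes +8 at w = 20%.

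**Dependence.** Take t = 60% and w of 20% and 10%. If worsening occurs only in participants who have another TEAE, the shift is 0. If it occurs only in those who do not, the shift is 10 points (80% against 70%). Independence gives 4.

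**Can the preferred-term table recover the figure?** No, because it gives marginal counts. In the second row, suppose all worsening is coded to one term. Subtracting that line from the total gives 68 − 20 = 48% on placebo and 64 − 10 = 54% on drug, a spurious 6-point excess on drug when the true value is 60% in both. The margins only bound the proportion with another TEAE: 48% to 68% on placebo and 54% to 64% on drug.

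**The case against.** The best counter-argument is that this is a convention, not an error. An AE is any untoward occurrence regardless of cause. Disease worsening qualifies, and it may be caused by the drug or follow its withdrawal. An endpoint of TEAE occurrence does not claim to measure only harm unrelated to efficacy, and removing worsening from it would drop possible drug-induced worsening from the main total. This stands, and it is why the endpoint should not be redefined.

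Other points also stand. Safety is descriptive, with no hypothesis test. The drug-related, SAE, AESI and discontinuation tables give other views. They do not supply the missing figure, though: relatedness rests on investigator judgement, and worsening can itself reach the SAE form. SAP 7.8.1 also refers to an internal sponsor guide on AE summaries that is not available here, so the finding is that no exclusion appears in the available text.

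A reader might infer more than the documents support:
- That worsening must be recorded as an AE. The text says should, although its place under the AE definition makes that the natural reading.
- That any effective drug will look safer. Worsening is an AN criterion and the primary endpoint is dT count, so a drug or dose acting mainly on dT would gain little. An effect on AN is plausible, because Protocol 1.2 hypothesises a direct effect on abscesses as well as tunnels, but it is not established.
- That exposure-adjusted rates are all distorted. SAP 7.8.1 defines them for a selected TEAE with its own time at risk, so worsening does not enter the rate of another selected event.
- That the any-TEAE total drives the dose choice. The objectives refer to available safety information in general.

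**Conclusion.** The point holds as a weakness in how safety is summarised. HS worsening is a lesion-count event listed for recording under the AE definition, and no available rule excludes it from the only Part 1 secondary safety endpoint. The any-TEAE and maximum-intensity comparisons therefore mix efficacy failure with other harms, and no other planned table shows how many participants had a TEAE other than HS worsening.

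The direction depends on spesolimab reducing AN worsening. The size rests wholly on assumed rates and independence: with 60% other TEAEs in both arms, 2 points (worsening 15% on placebo, 10% on drug) to 6 points (30%, 15%) in favour of the drug. It is zero if worsening is equal and other TEAEs do not differ. The documents do not show that the bias will occur or that it would decide the dose. They leave it possible and, with the planned tables, impossible to measure. This supports a cheap improvement to the SAP, not a change of endpoint.

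**What to change.** Leave AE recording and the all-inclusive TEAE endpoint as they are. In SAP 7.8.1, prespecify a supplementary overall and maximum-intensity TEAE summary, counted by subject, that excludes HS disease worsening, for the same periods as the main tables (to Week 8, to Week 16 and the whole on-treatment period). Show HS worsening on its own line by arm. State before unblinding how worsening is identified: a flag for events meeting the Section 4.2.3 definition, or a fixed list of study-disease preferred terms. Use both versions when safety is weighed in the Part 2 dose choice. The SAP has a close precedent: Section 7.2 takes rescue medication out of the concomitant-medication summary and reports it separately.

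The cost is one flag and a second version of the overview table. A flag tied to the protocol definition needs a link to AN counts or a CRF field. The preferred-term list avoids that but also removes HS events below the 150% threshold.
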